Day 25 through day 31 (7 days): 40 mg by mouth once daily

Day 32 through day 38 (7 days): 30 mg by mouth once daily

Day 39 through day 45 (7 days): 20 mg by mouth once daily

Day 46 through day 52 (7 days): 10 mg by mouth once daily

Day 53 through day 59 (7 days): 5 mg by mouth once daily.

If at the Month-2 visit (Visit 5.9), inflammation is observed, corticosteroid therapy should be re-initiated, via oral and/or intraocular route, based on the clinical condition of the subject, and the judgement of the investigator.

For pediatric subjects, oral prednisolone/prednisone will also be started 3 days prior to surgery. The starting dose will be based on kilogram weight of the subject, up to a maximum of 60 mg starting dose (rounded to the nearest 1 mg). Subsequent doses will have multipliers to provide the appropriate taper over an additional 6 weeks, for a total of 9 weeks of treatment. See tapering regimen for pediatric subjects below:

Day -3 through day 17 (21 days): Starting Dose (SD) 1 mg/kg by mouth/ once daily (maximum dose of 60 mg once daily)

Day 18 through day 24 (7 days): SD X 0.83 mg by mouth once daily

Day 25 through day 31 (7 days): SD X 0.67 mg by mouth once daily

Day 32 through day 38 (7 days): SD X 0.5 mg by mouth once daily

Day 39 through day 45 (7 days): SD X 0.33 mg by mouth once daily

Day 46 through day 52 (7 days): SD X 0.17 mg by mouth once daily

Day 53 through day 59 (7 days): SD X 0.08 mg by mouth once daily

If at the Month-2 visit (Visit 5.9), inflammation is observed, corticosteroid therapy should be reinitiated, via oral and/or intraocular route, based on the clinical condition of the subject, and the judgement of the investigator.

The local pediatric team should be involved with all children undergoing gene therapy surgery and should be available to give advice on the steroid doses used in each patient. Modifications of the protocol-defined steroid treatment are allowed based on the recommendation of the pediatric team, with approval from the Sponsor.

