For all subjects: while subjects are taking oral steroids, special note should be made to follow for potential side effects (e.g., increased IOP, cataracts, hypertension, elevated blood sugar, infections, gastritis/peptic ulcer disease, edema, electrolyte imbalance, mood changes, insomnia), and appropriate prophylaxis and/or therapy should be instituted as needed (e.g., treatment with proton pump inhibitors, valacyclovir; restriction of nonsteroidal anti-inflammatory agents).

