9.5. Visit 5 (Month 1 ± 7 Days)

At Visit 5, the following assessments will be performed:

- Collection of safety blood samples (hematology and clinical chemistry)
- Full ophthalmic examination, including indirect ophthalmoscopy, a slit-lamp examination, IOP, anterior chamber and vitreous inflammation grading and LOCS III cataract grading
- LLVA
- ETDRS BCVA
- SD-OCT
- Fundus autofluorescence
- MAIA microperimetry
- Viral shedding

- Immunogenicity sampling
- AE/SAE monitoring
- Review of concomitant medication, treatments, and procedures
- Corticosteroid compliance review¹
 - 1. Corticosteroid review is applicable only for treated subjects.

Where applicable, subjects will be reminded of the requirement to use barrier contraception or abstain from sexual intercourse for a period of 3 months from the time of treatment.

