11.2.2. Recording of Adverse Events

AEs/SAEs will be collected from the time the subject or parent / legal guardian (where applicable) provides written informed consent through Visit 11 (or ET Visit or Unscheduled Visits, if applicable).

AEs/SAEs that the investigator becomes aware of, and which are deemed to have a relationship to the study drug, should continue to be reported to NightstaRx following the completion of the study for a period of up to 5 years following surgery, until/unless the subject is enrolled in another NightstaRx study.

Subjects will be questioned on the occurrence of an AE at every visit including any unscheduled visit, by using non-leading questioning such as 'How have you been since the last visit?'

All AEs occurring during the study observed by the investigator or reported by the subject, whether attributed to study drug or the surgical procedure, will be recorded in the subject's medical records and in the eCRF. Any clinically significant changes in laboratory results or vital sign measurements (as determined by the investigator) are to be recorded as an AE.

The following information will be recorded in the eCRF for each AE: description, date of onset and end date, outcome, severity, assessment of relatedness to study drug/study procedure, the action taken and confirmation of whether the event is considered serious (see Section 11.2.1.2 for the definition of seriousness). Follow-up information should be provided as necessary (see Section 11.2.3 for specifics on follow-up procedures).

AE severity and relationship to the study drug or the surgical procedure will be assessed at the site by the investigator or a medically qualified designee.

AE Severity

The severity of events will be assessed on the following scale:

- 1. = mild (awareness of sign or symptom, but easily tolerated)
- 2. = moderate (discomfort sufficient to cause interference with normal activities)
- 3. = severe (incapacitating, with inability to perform normal activities).

AE Relationship

When assigning relatedness of the AE, consideration will be given to whether there is a plausible relationship to either the study drug or the surgical procedure. The following are definitions of relatedness that will be used in this study:

Unrelated: is not reasonably related in time to the administration of the

study drug/surgical procedure, or exposure of the study drug/surgical procedure has not yet occurred, or biologic

plausibility does not exist

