11.6. Vital Signs

Vital signs (pulse and systolic and diastolic blood pressure) will be taken at the times indicated in Table 3, Section 16.1. Vital signs should be taken after the subject is seated for at least 5 minutes.

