- b. Although the visit will still be considered out-of-window, if a subject in Part II is unable to attend the 12-month visit during the protocol-defined window, they should return to the site to complete this visit as soon as it is possible for them to do so. Delays will be identified as PDs on a case-by-case basis by the Sponsor based on information provided by the site; this will include but is not limited to scenarios such as site closure, travel bans, medical travel prohibitions, patient illness, etc.
- c. Visits 10 and 11 are for Part I subjects only

- d. Although the visit will still be considered out-of-window, if a subject in Part I is unable to attend the 24-month visit during the protocol-defined window, they should return to the site to complete this visit as soon as it is possible for them to do so. Delays will be identified as PDs on a case-by-case basis by the Sponsor based on information provided by the site; this will include but is not limited to scenarios such as site closure, travel bans, medical travel prohibitions, patient illness, etc.
- e. An early termination (ET) visit is to be performed if a subject discontinues at any time.
- f. If clinically indicated, subjects may need to return to the site for an unscheduled visit. At a minimum, the following assessments will be performed: full ophthalmic examination, BCVA, SD-OCT, microperimetry (if clinically feasible), fundus autofluorescence, AE/SAE monitoring, and concomitant medication, treatments, and procedures review
- g. Visits 2, 3, and 4 will be a telephone call only for subjects randomised to the control, untreated group. AE/SAE monitoring and concomitant medication, treatments, and procedures review will be assessed during the call.
- h. Includes hematology and clinical chemistry
- i. To be conducted only if unavailable at Visit 1
- j. Includes indirect ophthalmoscopy, slit lamp examination, IOP, anterior chamber and vitreous inflammation grading and LOCS III cataract grading
- k. Study eye only
- 1. Part I subjects will take 1 mg/kg/day prednisone/prednisolone for a total of 10 days (beginning 2 days before the vector injection, on the day of injection, and then for 7 days); followed by 0.5 mg/kg/day for 7 days; 0.25 mg/kg/day for 2 days; and 0.125 mg/kg/day for 2 days (21 days in total). Part II subjects in treated groups will be given a 9-week course of oral prednisone/prednisolone and instructed to start taking the drug 3 days before Visit 2. See Section 8.8.

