To improve safety and to prevent potential inflammatory response to therapy, the steroid regimen has been modified. A standardized adult starting dose of 60 mg has been selected (rather than the previous 1mg/kg starting dose) and the taper has been lengthened to include coverage out to approximately 2 months. A 2-month visit has been added to assess the subjects at the end of the steroid therapy.

Information on the procedures related to unmasking has been added to comply with Good Clinical practices. Serious adverse event reporting has also been changed to immediately instead of within 7 days, per regional recommendations.

From NSR-RPGR Version 7.0 to Version 7.1, this administrative protocol amendment clarifies the procedures and requirements for assessments done at each visit compared to the Schedule of Study Procedures. Footnotes for BCVA assessment, Immunogenicity sampling, and corticosteroid review were added to the in-text footnotes and Schedule of Study Procedures. In addition, Fundus photography was removed from Visit 6 and Visit 7, viral shedding was removed from Visit 6, and autofluorescence assessment was added to the Unscheduled Visit. Updates were made to the protocol to accommodate these changes.

CONFIDENTIAL Page 3 of 44

Page numbers on the following table of changes refer to the tracked changes version of the protocol amendment.

From Version 7.1 to Version 8.0, the unmasking information has been modified in Section 12.2.5 to adhere more closely to Good Clinical Practices. Also, the mobility test has been added to the Early termination Visit list of procedures, to be conducted if feasible.

Updates noted in italics are those referring to Version 7.0 to Version 7.1.

Updates noted in italics and bold, with grey shading, are those referring to Version 7.1 to Version 8.0.

CONFIDENTIAL Page 4 of 44

SUMMARY OF CHANGES PROTOCOL NSR-RPGR-01 Version 8.0, 18 DEC 2018			
Section, Page	Previous Text (Deleted Text Shown by Strikethrough)	Revised Text (Added Text Shown as Red)	Rationale

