	LLVA		Low luminance visual acuity testing removed; no rationale on first post-op day
Visit 4 (Day 7 Post- Operative Visit)	Blood pressure and pulse		No rationale for vitals on month 1, increases study burden on site
Visit 5 (Month 1)	Blood pressure and pulse		No rationale for vitals on month 1, increases study burden on site
Visit 9 (Year 1)	10.10 Visits 10 (Month 18 ± 14 Days) and 11 (Year 2 ± 14 Days, End of Study Visit)	10.10 Visit 10 (Month 18 ± 14 Days)	The procedures are no longer identical on these two visits so they have been separated

SUMMARY OF CHANGES PROTOCOL NSR-RPGR-01 Version 6.0, 18 MAY 2018			
Section, Page	Previous Text (Deleted Text Shown by Strikethrough)	Revised Text (Added Text Shown as Red)	Rationale
10.10 Visits 10 (Month 18 ± 14 Days) and 11 (Year 2 ± 14 Days, End of Study Visit)	Visual fields Contrast sensitivity test		These procedures have been removed from the visit to lessen the burden on the site.
10.10 Visit 10 (Month 18)	◆ ETDRS BCVA* ◆ LLVA* *Assessments collected in triplicate at Visit 11 (Year 2). To facilitate triplicate testing, the visit should be conducted over 2 days. It is recommended to measure BCVA and LLVA twice on the first day and once on the second day (prior to pupil dilation). All 3 BCVA and all 3 LLVA values must be recorded in the eCRF. LLVA should be conducted immediately after each BCVA assessment.	• ETDRS BCVA LLVA	These assessments are no longer done in triplicate on this visit to lessen the burden on the site.
		10.11 Visit 11 (Year 2 ± 14 Days, End of Study Visit) At Visits 11 the following ocular assessments will be performed: • Full ophthalmic examination, including indirect ophthalmoscopy, a slit-lamp examination, IOP, anterior chamber and vitreous inflammation grading and LOCS III cataract grading • ETDRS BCVA* • SD-OCT • LLVA* • Fundus autofluorescence • Microperimetry • Fundus photography • Visual Fields • Contrast sensitivity test	

SUMMARY OF CHANGES PROTOCOL NSR-RPGR-01 Version 6.0, 18 MAY 2018			
Section, Page	Previous Text (Deleted Text Shown by Strikethrough)	Revised Text (Added Text Shown as Red)	Rationale

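### Scheduled blood pressure stops at Day 7 of a Part II steroid course that runs to Day 59, although protocol 8.8 asks sites to follow hypertension

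*Protocol*

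**What the plan says.** Protocol 8.8 gives the Part II oral steroid regimen. Adults take 60 mg daily from Day -3 to Day 17 and then step down weekly; the last line is "Day 53 through day 59 (7 days): 5 mg by mouth once daily". Children follow the same days on a weight-based dose capped at 60 mg. The section closes with an instruction for the time on oral steroids: "special note should be made to follow for potential side effects (e.g., increased IOP, cataracts, hypertension, elevated blood sugar" and further effects, with prophylaxis or treatment as needed. It also directs that steroids be restarted if inflammation is seen at the Month 2 visit.

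Protocol 11.6 ties measurement to the schedule: "Vital signs (pulse and systolic and diastolic blood pressure) will be taken at the times indicated in Table 3". In Table 3 the blood pressure row is marked at screening, Day 0, Day 1 and Day 7, and nowhere later. The visit lists in 9.1 to 9.6 agree. Month 1 (9.5) and Month 2 (9.6) both list "Collection of safety blood samples (hematology and clinical chemistry)" and a full ophthalmic examination with intraocular pressure and lens grading, but no blood pressure. For the control group, Table 3 footnote g adds: "Visits 2, 3, and 4 will be a telephone call only for subjects randomised to the control, untreated group".

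SAP 7.13.9 plans observed values and change from baseline for blood pressure and heart rate, by treatment group and visit.

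**The concern.** A harm that the protocol names is measured on schedule only in the first part of the exposure that could cause it. Hypertension can be silent, so general questioning at visits may not bring it out. Protocol 11.2.2 requires clinically significant vital-sign changes to be recorded as adverse events, but that route needs someone to have taken a reading. A decision at Month 2 to restart steroids could be made with no protocol blood pressure since Day 7.

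The amendment history suggests a carry-over. The summaries of changes for Versions 4.0, 5.0 and 6.0 all log the removal of blood pressure and pulse at Month 1; the Version 6.0 reason is "No rationale for vitals on month 1, increases study burden on site". All three predate the nine-week course. Version 7.0 then lengthened the regimen, and its stated purpose for the new visit was this: "A 2-month visit has been added to assess the subjects at the end of the steroid therapy". Blood pressure was not added to that visit, nor put back at Month 1. At stake is the quality of steroid-safety monitoring in subjects who may be as young as 10.

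**Working it through.** **Inputs.** Dose days come from protocol 8.8; blood pressure marks and visit windows from Table 3; the earlier 21-day course from the Part I regimen in 8.8. Months are taken as 30 days (assumption), so Month 1 is Day 30 (window Day 23 to 37) and Month 2 is Day 60 (window Day 53 to 67).

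1. *Course length.* 59 - (-3) + 1 = 63 days. By segment, 21 + 6 × 7 = 63 days = 9 weeks, which reproduces the protocol's stated length.

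2. *Days after the last scheduled reading (Day 7).* Days 8 to 59 = 52 days, and 52/63 = 83%. Of these, Days 8 to 17 (10 days) are at 60 mg and Days 18 to 59 (42 days) are taper.

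3. *Adult dose after Day 7.* Total = 21 × 60 + 7 × (50 + 40 + 30 + 20 + 10 + 5) = 1260 + 1085 = 2345 mg. After Day 7 = 10 × 60 + 1085 = 1685 mg, or 72%.

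4. *Visit 4 window (Day 4 to 10).* A reading on Day 4 leaves 55 days (13 at 60 mg); on Day 10 it leaves 49 days (7 at 60 mg).

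5. *Why the old schedule fitted the old course.* The 21-day course ran from Day -2 to Day 18, with the full dose ending on Day 7. The earliest Month 1 visit, Day 23, came 5 days after the last dose. Under the 63-day course, Month 1 falls on 30 to 50 mg (40 mg on Day 30).

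6. *Effect of added readings on the longest run of course days without a reading.*

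| Schedule | Nominal days | Worst case in windows |
|---|---|---|
| Current | 52 (Days 8-59) | 55 (Days 5-59) |
| Month 1 added | 29 (Days 31-59; the earlier run, Days 8-29, is 22) | 36 (Month 1 on Day 23, so Days 24-59) |
| Months 1 and 2 added | 29 | 36 (Month 2 after Day 59) |

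The whole reduction comes from Month 1. Nominal Month 2 is one day after the last dose.

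7. *Controls.* They have 0 scheduled readings after screening now and would have 2 with both visits added.

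8. *Can it still help subjects in this trial?* The amendment summary for Version 11 puts the last enrolment at 30 September 2019. With the 12-week screening window fully used, the last Day 59 is 30 September 2019 + 84 + 59 days = 20 February 2020. If dosing ended at drug expiry (end of September 2019), it is about 28 November 2019. Both precede protocol Version 11 (1 October 2020) and SAP Version 4.0 (10 March 2021).

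**The case against.** The strongest reply is that 8.8 is a clinical-care instruction with an illustrative list, not a promise of scheduled tests. Mood change, insomnia and gastritis are on the same list and have no dedicated assessment either. Sites ask about adverse events at every visit and review concomitant medication, unscheduled readings are not barred, a paediatric team is involved for children, and the data monitoring committee reviews Part II safety. Protocol 11.2.2 covers "All AEs occurring during the study observed by the investigator or reported by the subject". This stands against anyone who infers that the protocol contradicts itself or that later hypertension would go unrecorded; the documents support neither. It does not remove the gap, because blood pressure, unlike insomnia, must be measured to be known.

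A second reply is that dropping Month 1 vital signs was deliberate: Version 4.0 cites reading-centre and site feedback that their utility was low. That is so, but the judgement was made under the 21-day course, and no logged reason revisits it for nine weeks.

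Third, controls take no steroid (Table 3 footnote l), so a reader who sees a steroid-safety gap in the control arm would be mistaken. Theirs is a comparison gap: scheduled data cannot supply the control change from baseline that SAP 7.13.9 calls for.

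Fourth, dosing is over. This stands in full and limits the point to further dosing under this schedule.

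**Conclusion.** The point holds as a cheap improvement to safety scheduling. After Day 7 there is no scheduled blood pressure for 52 of 63 course days (49 to 55 across the visit window), 10 of them at 60 mg, although 8.8 names hypertension as an effect to follow. The day counts rest on the protocol alone; the effect of the added readings also rests on 30-day months.

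A reader might extend the point to glucose, which 8.8 also names and which has no row in the markedly-abnormal table of SAP 7.13.10.1. The documents do not support a claim that glucose goes unmeasured or unanalysed. It is in the chemistry panel, drawn at Day 7 and Months 1, 2, 3 and 12, and is graded by CTCAE, flagged against normal ranges, shift-tabulated and listed. Only that one sponsor-defined summary omits it, as it omits 10 of the 19 panel analytes. No efficacy conclusion is affected.

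**What to change.** In protocol Table 3, 9.5 and 9.6, for any further dosing under this schedule:

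- Add blood pressure at the existing Month 1 visit. This supplies the whole cut in the longest unmeasured run.
- Add it at the existing Month 2 visit as an end-of-course check, taken before any decision to restart steroids.
- Do both in all arms, so that SAP 7.13.9 has a control change from baseline.

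The cost is one brief reading at each of two visits that subjects already attend. Days 8 to 17 at 60 mg stay uncovered because no visit falls there. Until the change is made, unscheduled readings and adverse-event reporting remain the means of detection.

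Optionally, add a sponsor-set high limit for non-fasting glucose to the markedly-abnormal table. That table counts a subject on any one post-baseline value, and treated subjects have a Day 7 sample that controls lack (five scheduled samples after screening against four). Any comparison between arms should therefore use samples from Month 1 onward. Non-fasting values will also produce some post-meal flags.

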8.9. Treatment Compliance

This study involves a single sub-retinal injection of up to 0.1 mL AAV8-RPGR. Measure of treatment compliance with AAV8-RPGR is therefore not necessary. The exact volume injected at the time of surgery should be recorded on the eCRF.

Compliance with the use of prednisone/prednisolone will be captured in the eCRF.

9. STUDY VISITS AND PROCEDURES

The schedule of study procedures is presented in Table 3, Section 16.1.

9.1. Visit 1 (Screening/Baseline Period)

The investigator will explain the study purpose, procedures, and subject responsibilities to each potential study subject. The subject's willingness and ability to meet the protocol requirements will be determined.

Prior to any study-specific procedure, written informed consent will be obtained. The subject or parent / legal guardian will sign and date 1 copy of the consent form in the presence of the investigator or his/her designee; where applicable, an assent form will be completed by the subject. The original signed form(s) will be retained at the study site and an additional copy will remain in the subject's medical records; a copy will also be given to the subject or parent / legal guardian.

After informed consent/assent has been obtained, the subject will be evaluated to determine eligibility. Screening assessments will be considered baseline measurements and will consist of the following:

- Demography
- Medical history, including ocular history
- Blood pressure and pulse
- Collection of safety blood samples (hematology and clinical chemistry)
- RPGR gene mutation screen (only if not conducted previously)
- Full ophthalmic examination, including indirect ophthalmoscopy, a slit-lamp examination, IOP, anterior chamber and vitreous inflammation grading and lens LOCS III cataract grading
- LLVA¹
- ETDRS BCVA^{1,2}
- SD-OCT
- Fundus autofluorescence
- MAIA microperimetry^{1,3}
- Fundus photography
- Octopus 900 visual fields^{3,4}
- Contrast sensitivity test¹
- •
- Viral shedding
- Immunogenicity sampling
- AE and SAE monitoring
- Review of medication, treatments, and procedures
- 1,6,7

• Randomisation⁶

1. In Part II, it is preferable that the same masked assessor who performs these assessments (LLVA, BCVA, microperimetry, contrast sensitivity and Month 3 through Month 12 also perform these assessments at screening.

2. For Part I subjects, BCVA is performed in triplicate at baseline. For Part II subjects, if the BCVA value at Visit 1 (Screening/Baseline) is $\geq \pm$ 10 letter gain or loss in the study eye compared to the previous XOLARIS study visit (if applicable), then BCVA must be repeated an additional 2 times, resulting in a total of 3 BCVA measures at Visit 1.

For Part II subjects, if the BCVA value at Visit 1 (Screening/Baseline) is $\leq \pm 10$ letter difference in the study eye compared to the previous XOLARIS study visit, then BCVA will be collected once and will not be repeated.

If subject was not previously in XOLARIS study, BCVA assessments at baseline must be performed in triplicate.

For all subjects who require triplicate BCVA testing, to facilitate the additional BCVA measures, this visit should be conducted over 2 days, with BCVA measured twice on Day 1 and once on Day 2 (prior to pupil dilation). All 3 BCVA values must be recorded in the eCRF. The highest score will be used to define subject eligibility.

- 3. Assessments at screening collected in triplicate. To facilitate triplicate testing, the visit should be conducted over 2 days. Visual field and microperimetry outputs will be sent to a CRC for review. Data will be generated and collated within the CRC and exported to the Sponsor or designee. For microperimetry, the last assessment performed during screening will be used for assessing eligibility and will be defined as the baseline assessment.
- 4. Octopus 900 perimeter is specified for visual field assessments only in Part II.

Subjects who meet all the inclusion criteria and none of the exclusion criteria will have a study eye assigned and be enrolled into the study. In Part II, subjects will be informed of the randomisation outcome (i.e., AAV8-RPGR treatment or the Control group) and instructed to not reveal their treatment group assignment to the masked assessors during the study. Subjects randomised to the AAV8-RPGR treatment groups (along with the Investigators and sponsor) will remain masked to the assigned dose.

See Section 8.5 for details on randomisation and assignment of subject numbers.

The next study visit (Visit 2) is to be scheduled within 12 weeks of the Screening/Baseline Visit. Subjects will be given a course of oral prednisone/prednisolone and instructed to start taking the drug 2 days (Part I) or 3 days (Part II) before their next study visit (Visit 2). Where applicable, subjects will also be instructed to use barrier contraception or abstain from sexual intercourse for a period of 3 months from the time they are treated.

